11.5 Local Tolerability

Local tolerability of the subcutaneous injection will be assessed by the investigator according to 6 items: swelling, induration, heat, redness, pain, and other findings. Number and proportion of subjects reporting each condition will be summarized.

11.6 Safety Subgroup Analysis

For RZB, RZB_NL, Retreatment and UST_RZB Populations, AE overview tables will be provided in the subgroup including subjects from Japan only. This subgroup analysis will only be performed in the final analysis, upon study completion.

In addition, the number and percentage, as well as exposure adjusted event rate of hypersensitivity events and injection site reactions will also be summarized among the ALL_RZB Population (150 mg), by the anti-drug antibody (ADA) status during the analysis period.

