11.0 Safety Analysis

11.1 General Considerations

Safety analyses will include adverse events, laboratory, local tolerability, and vital sign measurements.

For the safety analyses, a baseline value (BL_RZB) is defined as the last non-missing observation on or prior to the date of the first dose of Risankizumab either in Study M15-997 or the preceding studies whichever is the earlier.

For subjects from Japan among the RZB, RZB_NL, Retreatment and UST_RZB Populations, only data prior to the start of risankizumab 75 mg dose will be used in the safety analyses. This subgroup analysis will only be performed in the final analysis, upon study completion.

When summarizing the safety for risankizumab 150 mg among the ALL_RZB Population, safety data collected (i) from feeder studies not using risankizumab 150 mg dose and/or (ii) from subjects in Japan who have started the risankizumab 75 mg dose will not be included for the safety summary of risankizumab 150 mg dose.

For the RZB Japan Population, safety data will be summarized regardless of dose.

Summaries of treatment-emergent adverse events (TEAEs), potentially clinically important laboratory values and vital sign values, and liver function tests will be provided for all populations. Analysis of change from baseline in laboratory values and vital sign values, shift tables and local tolerability will be provided for RZB, RZB_NL, UST_RZB, ADA_RZB, FUM_RZB, RZB Japan populations.

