11.2 Analysis of Adverse Events

11.2.1 Treatment-Emergent Adverse Events

Treatment emergent adverse events (TEAEs) are defined as any event with an onset date that is after the first dose of risankizumab and with an onset date within 140 days after the last dose of study drug in the analysis period except:

- **TEAE of Retreatment:** TEAE are defined as any event with an onset date that is after the first dose of retreatment and no more than 140 days after the last dose of study drug, and prior to the start of risankizumab 75 mg (if any, for subjects in Japan).
- **TEAE of ALL_RZB (any dose):** TEAEs are defined as any event with an onset date after the first dose of risankizumab through 140 days after the last dose of risankizumab, except for AEs with an onset date during protocol-designed treatment gaps (i.e., placebo period in subjects re-randomized to placebo during Study 1311.4 Part B) that was more than 140 days from the last dose of previous risankizumab treatment and before the first dose of retreatment in the ALL_RZB Population.
- **TEAE of RZB, RZB_NL, UST_RZB, ADA_RZB, FUM_RZB and ALL_RZB (150 mg):** TEAEs are defined as any event with an onset date after the first dose of risankizumab 150 mg through 140 days after the last dose of risankizumab 150 mg, and prior to the start of risankizumab 75 mg (if any, for subjects in Japan), except for AEs with an onset date during protocol-designed treatment gaps (i.e., placebo period in subjects re-randomized to placebo during Study 1311.4 Part B) that was more than 140 days from the last dose of

previous risankizumab 150 mg treatment and before the first dose of retreatment in the ALL_RZB Population.

Events where the onset date is the same as the study drug start date are assumed to be treatment emergent, unless the adverse event start time is prior to the study drug start time. If an incomplete onset date is collected for an adverse event, the event will be assumed to be treatment-emergent unless there is other evidence that confirms that the event is not treatment-emergent (e.g., the event end date is prior to the study drug start date).

The number and percent of subjects experiencing treatment-emergent TEAEs will be tabulated using the Medical Dictionary for Drug Regulatory Activities (MedDRA[®]) system organ class and preferred term.

Summary tables will be presented as follows:

1. Adverse Event Overview

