The number and percentage of subjects experiencing treatment-emergent adverse events will be summarized for the following adverse event categories:

- Any AE
- Any AE that was assessed as related to study drug by the investigator
- Any severe AE
- Any serious AE
- Any serious AE that was assessed as related to study drug by the investigator
- Any AE leading to discontinuation of study drug
- Any AE leading to death
- Any deaths
- Areas of Safety Interest
- Any COVID-19 Related AE

2. Adverse Events by System Organ Class and Preferred Term

TEAEs will also be summarized and presented using primary Medical Dictionary for Regulatory Activities (MedDRA) system organ classes (SOCs) and preferred terms (PTs). The SOCs will be presented in alphabetical order, and the PTs will be presented in alphabetical order within each SOC.

Subjects reporting more than one adverse event for a given MedDRA preferred term will be counted only once for that term (most severe incident for the severity tables and most related incident for the relationship tables). Subjects reporting more than one type of adverse event within a SOC will be counted only once for that SOC. Subjects reporting more than one type of adverse event will be counted only once in the overall total.

In addition, the number and percentage of adverse events with causal relationship between the events and the study drug will be summarized using the same conventions described above.

3. Adverse Events by Maximum Severity

The severity grading of AEs follows Rheumatology Common Toxicity Criteria (RCTC).

- Grade 1 – mild
- Grade 2 – moderate
- Grade 3 – severe
- Grade 4 – life threatening

Adverse events will also be summarized by maximum severity. If a subject has an adverse event with unknown severity, then the subject will be counted in the severity category of "unknown," even if the subject has another occurrence of the same event with a severity present. The only exception is if the subject has another occurrence of the same adverse event with the most extreme severity – ("Life-threatening"). In this case, the subject will be counted under the "Life-threatening" category.

4. Adverse Events by Maximum Relationship

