Serious Infections	Serious AEs in the Infections and Infestations SOC	
Active Tuberculosis	Active Tuberculosis CMQ (code 80000188)	
Opportunistic Infections excluding tuberculosis and herpes zoster	Opportunistic infection excluding tuberculosis and herpes zoster CMQ (code 80000189)	
Injection Site Reactions	Narrow	Injection site reaction CMQ (code 80000019)
Malignancies	Narrow	Malignant tumours (SMQ 20000194)
Non-melanoma Skin Cancer (NMSC)	Broad	Skin malignant tumours (SMQ 20000204) excluding terms identified by the Melanoma CMQ (code 80000119)
Malignant Tumours excluding NMSC	'Malignant Tumours excluding NMSC' is identified by the 'Malignant Tumours' search excluding terms identified by the 'Non-melanoma skin cancer (NMSC)' search.	
Hypersensitivity	Narrow	Hypersensitivity (SMQ 20000214)
Serious hypersensitivity reactions	Narrow	Serious AEs in the Hypersensitivity (SMQ 20000214)
Adjudicated Anaphylactic Reaction*	Adjudicated terms will be identified using SDTM data (e.g., CE and PR domains).	
Hepatic Events	Broad	Hepatic failure, fibrosis and cirrhosis and other liver damage-related conditions (SMQ 20000013)
	Broad	Hepatitis, non-infectious (SMQ 20000010)
	Broad	Cholestasis and jaundice of hepatic origin (SMQ 20000009)
	Broad	Liver related investigations, signs and symptoms (SMQ 20000008)
	Narrow	Liver-related coagulation and bleeding disturbances (SMQ 20000015)

* Events will be identified for adjudication by Anaphylactic Reaction SMQ Broad search as specified in the RISA AAC Charter.

Adverse Event per 100 Patient-Years of Exposure

Adverse events occurring during the analysis period for each population will be presented by event rate per 100 patient-years. These will be presented for any TEAEs, serious adverse events, Areas of Special Interest.

AEs per 100 patient-years of exposure is defined as the number of AEs divided by the total exposure in 100 patient-years. Note that one event per preferred term per day per subject will be counted in the calculation of the number of AEs (i.e., a preferred term will not be counted twice on the same day for the same subject). See the calculation method below.

$$100 \times \frac{\text{Number of TEAEs}}{\text{Total Patient Years}}$$

where total patient years is defined as the sum of the study drug exposure (defined as date of last dose – date of first dose + 140 days (5 half-lives)) of all subjects normalized by 365.25, and rounded to one decimal place.

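### SAP 11.6 plans only crude AE percentages for the Japan-only subgroup, although Japanese follow-up is cut at the start of 75 mg; uncommon events will be understated unless a rate with a matching cut is added.

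*SAP*

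**What the plan says.** The Japan-only safety subgroup applies to four populations (RZB, RZB_NL, Retreatment, UST_RZB) and is produced at the final analysis only. SAP 11.6 describes its content in one clause: "AE overview tables will be provided in the subgroup including subjects from Japan only". SAP 11.2.1 defines that overview: "The number and percentage of subjects experiencing treatment-emergent adverse events will be summarized for the following adverse event categories". No rate appears in the definition.

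For Japanese subjects in the same four populations, SAP 11.1 states that "only data prior to the start of risankizumab 75 mg dose will be used in the safety analyses". The treatment-emergent definitions in 11.2.1 carry the same stop, worded "and prior to the start of risankizumab 75 mg (if any, for subjects in Japan". It therefore applies only to those who start 75 mg.

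Rates are planned elsewhere. SAP 11.2.1 states: "Adverse events occurring during the analysis period for each population will be presented by event rate per 100 patient-years". The patient-years behind these rates are "date of last dose – date of first dose + 140 days (5 half-lives", summed over subjects. In 11.6 itself, the paragraph after the Japan subgroup deals with anti-drug-antibody status, and there "the number and percentage, as well as exposure adjusted event rate of hypersensitivity events and injection site reactions will also be summarized".

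A separate RZB Japan Population (SAP 5.1) covers the extension period regardless of dose.

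**The concern.** A crude percentage can be compared between groups only if they were observed for similar lengths of time. Here the plan shortens observation for some Japanese subjects by rule and leaves the other members of the same populations uncut. The table chosen to describe the Japanese subjects is the one format that does not account for observation time.

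The study is descriptive throughout and its primary objective is long-term safety, so these displays are themselves the result. A reader who lays the Japan overview beside the parent population's could take a shortfall in serious AEs or areas of safety interest as a regional difference when part or all of it is shorter observation. The antibody paragraph shows that the SAP writes out an exposure-adjusted rate for a subgroup where one is wanted. None is written for Japan.

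**Working it through.** **No figure to reproduce.** The documents state no AE rate, no number of Japanese subjects starting 75 mg and no start date. What follows is an illustration; every input marked *assumed* is mine.

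**1. Full-course follow-up.** The last analysis windows in SAP 6.0 differ by population. Adding the 140-day tail and dividing by 365.25:

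| Population (SAP table) | Last window | Days | Years |
|---|---|---|---|
| RZB (Table 1) | Week 304 | 304×7 + 140 = 2268 | 6.21 |
| Retreatment, relapsed (Table 5) | Week 292R | 292×7 + 140 = 2184 | 5.98 |
| RZB_NL (Table 3) | Week 288S | 288×7 + 140 = 2156 | 5.90 |
| Retreatment, retreated in the extension (Table 6) | Week 252R | 252×7 + 140 = 1904 | 5.21 |
| UST_RZB (Table 10) | Week 252 | 252×7 + 140 = 1904 | 5.21 |

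These are maximum courses without dropout, not means.

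**2. Crude percentage under equal risk.** Percentage = 1 − exp(−rate × T), with the same constant rate in everyone (*assumed*). T is the full course, or the time to an *assumed* 75 mg start at Week 104, 156, 208 or 260 after first risankizumab dose (1.99, 2.99, 3.99 or 4.98 years). RZB, with every Japanese subject cut (*assumed*):

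| Rate per 100 PY (*assumed*) | Wk 104 | Wk 156 | Wk 208 | Wk 260 | Full course |
|---|---|---|---|---|---|
| 1 | 2.0% | 2.9% | 3.9% | 4.9% | 6.0% |
| 3 | 5.8% | 8.6% | 11.3% | 13.9% | 17.0% |
| 8 | 14.7% | 21.3% | 27.3% | 32.9% | 39.1% |
| 50 | 63.1% | 77.6% | 86.4% | 91.7% | 95.5% |
| 150 | 95.0% | 98.9% | 99.7% | 99.9% | 100.0% |

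Example: 1 − exp(−0.03 × 2.99) = 8.6%; 1 − exp(−0.03 × 6.21) = 17.0%.

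**3. Only some subjects switch.** If half switch (*assumed*), the 3 per 100 row is the average of cut and full-course values: 11.4%, 12.8%, 14.1%, 15.4%, against 17.0%.

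**4. Shorter populations.** For UST_RZB the full-course value at 3 per 100 is 1 − exp(−0.03 × 5.21) = 14.5%, so the gap is smaller: 8.6% against 14.5% for a Week 156 cut.

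**5. A rate, with and without a matching denominator.** If events and time both stop at the 75 mg start, the expected rate equals the true one at any cut (3.0 stays 3.0). If events stop but the denominator runs to the last dose plus 140 days, the displayed rate is true rate × T(cut)/T(full). For RZB at a true 3.0 this gives 0.96, 1.44, 1.93 or 2.41 for cuts at Week 104, 156, 208 or 260. For example, 3.0 × 2.99/6.21 = 1.44. The written formula has no stop at 75 mg, so adding a rate without changing the denominator would bring the same downward bias back.

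**The case against.** Four objections have weight.

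*11.6 does not exclude rates.* It is silent rather than prohibitive. Protocol 8.1.5 pairs percentages with events per 100 patient-years for serious AEs, deaths, discontinuations and AESIs. Several shells in SAP Appendix A come as an n (%) table plus an events-per-100-PY table, and the full table list is in a separate document. Rates may therefore be produced. This stands as a caution. Even so, the subgroup is not one of the populations for which 11.2.1 promises rates, and the denominator formula would still need the stop.

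*Japanese rates are planned anyway.* The RZB Japan Population is a defined analysis population, so rates for it follow from 11.2.1, without the 75 mg cut. A reader might infer from 11.6 alone that a higher Japanese risk would stay hidden. The documents do not support that, because this population partly answers the regional question. However, it mixes doses and covers only the extension, so it does not correct the 150 mg subgroup tables.

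*No Japan-versus-rest comparison is planned and nothing is tested.* That is correct. The harm is to descriptive reading, not to a formal inference. The parent population also contains the cut Japanese subjects, so its own percentage is slightly lowered too.

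*The size is unknown.* This is also correct. The SAP says if any, and the illustration sets a cut course against a maximum one. Dropout would narrow the gap.

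**Conclusion.** The point holds as a bias of known direction and unknown size. Under equal risk, Japanese subjects cut at 75 mg contribute fewer first events to an unchanged denominator, so percentages for uncommon events are too low relative to the parent population. How much too low depends on how many switch and when.

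At an assumed 3 per 100 patient-years in RZB, the shortfall from 17.0% runs from 1.6 points (half switch, cut at Week 260: 15.4%) to 11.2 points (all switch, cut at Week 104: 5.8%). It is smaller in populations with shorter courses and approaches nil if few switch. At 150 per 100 patient-years, any cut from Week 156 costs at most about one point, so an any-AE row that is already near saturation is little affected.

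A reader might go further and say that every Japanese percentage will come out lower, or that all non-Japanese subjects are followed to Week 304. Neither is supported. The cut reaches only those who start 75 mg, a true difference in AE rates could offset or add to the effect, and Week 304 applies to RZB alone.

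**What to change.** - **SAP 11.6:** add events per 100 patient-years to each row of the Japan-only AE overview, beside the number and percentage.
- **SAP 11.2.1:** state that, where events are cut at the start of 75 mg, patient-years are cut at the same date. This also keeps the parent populations' rates consistent, since they include the same Japanese subjects. Section 9.0 defines exposure with an 84-day tail and also has no stop at 75 mg; say which definition feeds which table.
- **Reporting:** show N, the number cut at 75 mg, total patient-years and median follow-up for the Japan subgroup beside the parent population, so that the actual size of the effect is visible.

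The cost is a few sentences in the SAP and one extra column per overview table at the final analysis, with no new data collected. The downside is that rates in small Japanese cells will be imprecise.

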1. Subjects with moderate to severe chronic plaque psoriasis who have completed one of the preceding Studies 1311.3, 1311.4, 1311.13, 1311.28, 1311.30, 1311.38 and M16-178.	
2. Subjects must be candidates for prolonged open label risankizumab treatment according to investigator judgment	
Main Exclusion:	
1. Premature discontinuation for any reason in the preceding study.	
Investigational Product:	Risankizumab (ABBV-066): 75 mg pre-filled syringe, 90 mg/mL, 0.83 mL dispensed volume, 0.87 mL fill volume
Dose:	Risankizumab (ABBV-066): 150 mg administered every 12 weeks
Mode of Administration:	Subcutaneous injection
Duration of Treatment: The study duration is 252 weeks.	
Criteria for Evaluation:	
Efficacy:	
Key variables to be summarized at all visits:	

• Proportion of subjects achieving $\geq 90\%$ reduction in Psoriasis Area and Severity Index (PASI) score (PASI 90)• Proportion of subjects achieving the Static Physician Global Assessment (sPGA) score of clear or almost clear• Proportion of subjects achieving $\geq 75\%$ reduction in PASI score (PASI 75)• Proportion of subjects achieving 100% reduction in PASI score (PASI 100)• Proportion of subjects achieving the sPGA score of clear	
Pharmacokinetics (PK) and Immunogenicity:	
Blood samples will be collected for measurement of risankizumab concentration and anti-drug antibody (ADA) and neutralizing antibody (NAb) just prior to dosing at Baseline, Week 48, Week 96, Week 156, Week 204 and End of Treatment (EOT) visit.	
Safety:	
Adverse events (AE)s, laboratory data and vital signs will be assessed throughout the study.	
Statistical Methods:	
Efficacy:	
For all efficacy analyses (including the assessment of PASI responses), baseline refers to the last non-missing value prior to the first dose of study drug in the preceding studies.	
Summary statistics will be provided. Continuous variables will be summarized by the number of observations, mean, standard deviation, median, minimum, maximum, 25 th and 75 th percentile, as well as the 95% confidence intervals (CIs) of mean values. Categorical variables will be summarized by counts and percentages, as well as the 95% CIs of the percentages.	

Statistical Methods (Continued):

Pharmacokinetics (PK) and Immunogenicity:

Risankizumab plasma concentrations will be determined. Descriptive statistics will be calculated for each sampling time (study visit). The number and percentage of subjects with ADA will be calculated.

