external Anaphylaxis Adjudication Committee (AAC) will be adjudicating observed suspected anaphylactic reactions and will remain blinded to treatment allocation. The events that are adjudicated and the adjudication process will be detailed in the Anaphylaxis Adjudication Committee Charter. A supplemental Hypersensitivity/Anaphylactic reactions eCRF will be used to collect information pertinent to the events. In addition, the site may be contacted for additional source documentation for relevant events.

In the event of a suspected systemic post-dose hypersensitivity reaction, a PK, ADA, and NAb sample should be collected once within 24 hours of the reaction. In addition to PK, ADA and NAb assays, blood tests to be conducted in the event of a systemic hypersensitivity reaction are:

- Serum tryptase: Optimally, measurement needs to be obtained from 15 minutes to 3 hours of symptom onset, and no later than 6 hours (as tryptase may remain elevated for 6 or more hours after the onset and therefore may still be informative if obtained after 3 hours); it is also requested to collect a follow-up tryptase level a minimum of 2 weeks after the recorded event or at the next study visit
- Plasma histamine: optimally, within 5 to 15 minutes of the onset of symptoms, and no later than 1 hour

Subjects will be given instructions regarding management of signs and symptoms of anaphylaxis to be followed during home dosing at Weeks 168, 192, 216 and 240.

Hypersensitivity reactions should be treated according to medical standards. Any events of hypersensitivity should be reported as an adverse event on the AE eCRF and additionally the supplemental hypersensitivity reaction eCRF should be completed. Pre-medications for further injections might be considered and will be agreed on between investigator and the AbbVie TA MD.

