Program Source Code: /[name]/SDA/ABBV-066/Psoriasis/CSR/M15-997/G/14.3/PCMS_RUN/s1311_31_aesi.sas

Table 14.3__2
Subjects with Treatment-Emergent AESI
(RZB Population)

Category MEDDRA 20.0 Preferred Term	RZB (N=) n (%)
<hr/>	
Subjects with:	
Fungal Infections	
...	XXX (XX.X)
...	XXX (XX.X)
Herpes Zoster	XXX (XX.X)
...	XXX (XX.X)

Program Source Code: /[name]/SDA/ABBV-066/Psoriasis/CSR/M15-997/G/14.3/PCMS_RUN/s1311_31_aesi.sas

Table 14.3__3
 Subjects with Treatment-Emergent Hypersensitivity by Subgroup
 (RZB Population)

Subgroup	RZB
Status	(N=)
Category	n (%)
MEDDRA 20.0 Preferred Term	
<hr/>	
Antidrug Antibody Positive Status (Yes, No)	
Yes	
Hypersensitivity	XXX (XX.X)
xxx	XXX (XX.X)
...	XXX (XX.X)
Anaphylactic Reaction	XXX (XX.X)
...	XXX (XX.X)
No	
Hypersensitivity	XXX (XX.X)
xxx	XXX (XX.X)

Program Source Code: /[name]/SDA/ABV-066/Psoriasis/CSR/M15-997/G/14.3/PCMS_RUN/s1311_31_aesi.sas

Table 14.3_4
 Subjects with Treatment-Emergent Injection Site Reaction by Subgroup
 (RZB Population)

Subgroup	RZB
Status	(N=)
MEDDRA 20.0 Preferred Term	n (%)
Antidrug Antibody Positive Status (Yes, No)	
Yes	XXX (XX.X)
xxx	XXX (XX.X)
No	XXX (XX.X)
xxx	XXX (XX.X)

Program Source Code: /[name]/SDA/ABV-066/Psoriasis/CSR/M15-997/G/14.3/PCMS_RUN/s1311_31_aesi.sas

Table 14.3__5
 Treatment-Emergent Adjudicated CV Adverse Events
 (RZB Population)

Category Sub-Category	RZB (N=) (PYS=) Events (E/100PY)
Subjects with:	
MACE	
Myocardial Infarction	XXX (XX.X)
...	XXX (XX.X)
Extended MACE	XXX (XX.X)
Myocardial Infarction	XXX (XX.X)
...	XXX (XX.X)
Other CV Events	XXX (XX.X)

Program Source Code: /[name]/SDA/ABBV-066/Psoriasis/CSR/M15-997/G/14.3/PCMS_RUN/s1311_31_aesipy.sas

Table 14.3__6
 Treatment-Emergent AESI
 (RZB Population)

Category MEDDRA 20.0 Preferred Term	RZB (N=) (PYS=) Events (E/100PY)
Subjects with:	
Fungal Infections	XXX (XX.X)
...	XXX (XX.X)
...	XXX (XX.X)
Herpes Zoster	XXX (XX.X)
...	XXX (XX.X)

Program Source Code: /[name]/SDA/ABBV-066/Psoriasis/CSR/M15-997/G/14.3/PCMS_RUN/s1311_31_aesipy.sas

Table 14.3__7
 Treatment-Emergent Hypersensitivity by Subgroup
 (RZB Population)

Subgroup	RZB
Status	(N=)
Category	(PYS=)
MEDDRA 20.0 Preferred Term	Events (E/100PY)
Antidrug Antibody Positive Status (Yes, No)	
Yes	
Hypersensitivity	XXX (XX.X)
Dermatitis	XXX (XX.X)
...	XXX (XX.X)
Anaphylactic Reaction	XXX (XX.X)
...	XXX (XX.X)

Program Source Code: /[name]/SDA/ABV-066/Psoriasis/CSR/M15-997/G/14.3/PCMS_RUN/s1311_31_aesipy.sas

Table 14.3__8

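### The ADA-status safety tables in SAP 11.6 credit reactions and exposure before the first positive sample to the ADA-positive group, and do not say whether reaction-triggered samples count

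*SAP*

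**What the plan says.** - **Subgroup.** SAP 11.6 plans the number, the percentage and the "exposure adjusted event rate of hypersensitivity events and injection site reactions will also be summarized among the ALL_RZB Population (150 mg"). The grouping variable in that sentence is worded "by the anti-drug antibody (ADA) status during the analysis period". It gives no rule for eligible samples, unscheduled samples, timing relative to the event, or missing results.
- **Shells.** SAP Appendix A shows one level, "Antidrug Antibody Positive Status (Yes, No"), with a patient-year total in the rate shell. These shells are titled for the RZB Population, whereas 11.6 names ALL_RZB (150 mg).
- **Numerator.** For ALL_RZB (150 mg), SAP 11.2.1 counts "any event with an onset date after the first dose of risankizumab 150 mg through 140 days after the last dose of risankizumab", where the last dose is again one of 150 mg. The exceptions concern the Japanese 75 mg dose and the Study 1311.4 placebo gap, not ADA onset.
- **Denominator.** SAP 11.2.1 continues "where total patient years is defined as the sum of the study drug exposure", which runs from first dose to last dose plus 140 days.
- **Scheduled sampling.** The protocol synopsis places ADA samples "just prior to dosing at Baseline, Week 48, Week 96, Week 156, Week 204 and End of Treatment (EOT) visit".
- **Triggered sampling.** For a suspected systemic post-dose hypersensitivity reaction, protocol 5.3.1.1 says "a PK, ADA, and NAb sample should be collected once within 24 hours of the reaction".
- **Contrast.** The efficacy subgroup in SAP 10.5 fixes ADA status by Week 208 and by Week 256. The safety subgroup has no such anchor.

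**The concern.** A reader will use these tables to judge whether anti-drug antibodies go with hypersensitivity or injection-site reactions. For that, the order of antibody and event matters. With one label for the whole period, a reaction in year 1 of a subject who first tests positive in year 4 appears as a reaction in an ADA-positive subject, and the intervening years enter the ADA-positive denominator. A real link could be understated, in a study whose primary objective is long-term safety.

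The second issue is sampling that depends on the outcome. If the triggered sample counts toward the status, a subject who reacts gets an extra chance to be classified positive because of the reaction. That pushes the hypersensitivity comparison the other way.

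**Working it through.** The documents give no ADA incidence, reaction rate or expected ratio, so there is no plan figure to reproduce. The sizes below are illustrative.

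**1. Exposure before detection.** A subject dosed through Week 252 has 252 + 20 = 272 weeks of OLE exposure, because 140 days are added. If the first positive sample is at Week 96, the share before it is 96/272 = 35%. If the Week 48 sample was negative, true onset lies between 48/272 = 18% and 35% of that exposure. Time on risankizumab 150 mg in the preceding study comes on top.

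**2. Effect on the rate ratio, persistent ADA.** Let *f* be the share of exposure before onset, *R* the true ratio, and the background rate constant. The whole-period ratio is approximately *f* + (1 − *f*)*R*.

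| *f* | *R* = 3 | *R* = 1 |
|---|---|---|
| 48/272 = 0.18 | 0.18 + 0.82 × 3 = 2.6 | 1 |
| 96/272 = 0.35 | 0.35 + 0.65 × 3 = 2.3 | 1 |
| 204/272 = 0.75 | 0.75 + 0.25 × 3 = 1.5 | 1 |

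A true association shrinks. A null ratio does not move, because events and time are reassigned together.

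**3. Simulation.** From the documents: samples at Weeks 0, 48, 96, 156, 204 and 252, exposure to last dose plus 20 weeks, and 2200 subjects (15 replicates per scenario). Assumed: 5 events per 100 patient-years while ADA-negative, 5% dropout per year, and ADA onset at 6% per year (persistent) or 10% per year (transient).

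| Scenario | Share of events triggering a sample | Whole-period, scheduled samples | Whole-period, with triggered samples |
|---|---|---|---|
| True ratio 3, persistent | 10% | 2.17 | 2.18 |
| True ratio 3, lasting 24 weeks | 10% | 1.335 | 1.362 |
| True ratio 1, lasting 12 weeks | 10% | 1.019 | 1.035 |
| True ratio 1, lasting 12 weeks | 50% | 1.025 | 1.073 |
| True ratio 1, lasting 12 weeks | 100% | 1.051 | 1.152 |

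A further run of the persistent case gave about 2.1. At 10% triggering the shift is 0.01 to 0.03. At 100% it is 1.152 − 1.051 = 0.10.

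**4. What a split recovers.** Splitting by true current ADA state, which cannot be observed, returns 3.04 (persistent) and 2.96 (24 weeks). Splitting at the first positive scheduled sample, which can be programmed, returns about 2.8 if ADA persists but only about 1.3 if it lasts 24 weeks. If reactions are concentrated early, that split gives a ratio near 0.7 with no true effect, because ADA-positive time falls later.

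**5. Percentages.** With no true effect, the ratio of the percentages of subjects with an event is already 1.12 to 1.15 on scheduled samples. Longer follow-up raises the chance of both a positive sample and an event.

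**The case against.** A reader might infer that the SAP counts reaction-triggered samples and so builds in a false positive association for both outcomes. The documents do not support that. No section says these samples feed the subgroup variable. Protocol 5.3.1.1 shows that they are taken and meant to be assayed, while the explicit commitment in protocol 5.3.2.4 covers samples at the Appendix C visits. The trigger is a suspected systemic reaction, so it cannot affect injection-site reactions. The hypersensitivity category is a narrow SMQ, and not every event in it need be a suspected systemic post-dose reaction.

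A reader might also compare seven samples with six. With per-sample positivity *q* (assumed), ever-positive is 1 − (1 − *q*)^6 against 1 − (1 − *q*)^7: 11.4% against 13.2% at *q* = 2%, and 46.9% against 52.2% at *q* = 10%, odds ratios of 1.18 and 1.24. This requires every reactor to be sampled and results to be independent. If 10% are sampled, ever-positive in reactors is 11.4 + 0.1 × 1.8 = 11.6%, or 46.9 + 0.1 × 5.3 = 47.4%, and the odds ratio is about 1.02. The count of six also covers the OLE only; preceding-study schedules are not in these documents.

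Two further objections stand. The tables are descriptive and no statistical test is planned. And splitting at the first positive sample misplaces events between true onset and detection, so it should not replace the planned table. Neither removes the timing problem.

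**Conclusion.** The timing defect follows from the text: one label per subject, with a numerator and denominator that ignore ADA onset. It affects both outcomes and mainly dilutes a true association. On the assumptions above, 3 becomes about 2.1 with persistent ADA and about 1.3 with ADA lasting 24 weeks. It does not create an association in the event rates when there is none and the rate is constant.

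The handling of triggered samples is an undefined rule, not a stated error. It concerns hypersensitivity only, and its likely effect is small unless most events trigger a sample and ADA is transient. The two mechanisms pull in opposite directions, so the table cannot be read with confidence until the rule is written. As a descriptive subgroup summary, this merits correction but does not threaten the main safety results.

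**What to change.** In SAP 11.6:

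1. Keep the planned table, with ADA status defined from scheduled samples. Show subjects positive only on a reaction-triggered sample separately, so that the sample closest to the reaction is not lost.
2. For every event in an ADA-positive subject, show whether onset was before or after the first positive sample.
3. Add a supplementary rate with events and patient-years split at the first positive scheduled sample.
4. State how missing ADA results are handled, and align the population in the shell titles with the text.

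The cost is a few sentences and modest programming, with no new data. The downside is that onset is known only to within the 48 to 60 week sampling gap, and ADA-positive time falls later in follow-up. The split rate should therefore stay supplementary and be read by time period if reaction rates fall over time.
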